1.4 Clinical Trials

Pharmacokinetic data collected during studies conducted by Sonus were analyzed by NuvOx^{16,17}. The pharmacokinetics of DDFP in human subjects exhibits biphasic decline after an IV bolus dose; there is a rapid initial decline followed by a slow terminal elimination phase¹⁷. The terminal elimination phase ($t_{1/2}$) in humans ranges from 81-99.5 min for doses of 0.15-0.35 mL/kg. The values of half-life in dogs (30-48 min) were shorter than humans. The half-life is the shortest in rats (0.7-1.9 min). Efficacy was demonstrated in lower levels in animal stroke models and higher levels are not thought necessary in humans.

DDFP is not metabolized in humans. The major route of excretion of DDFP is through expired air. Almost one hundred percent of administered dose was recovered in the expired air as DDFP. The clearance of DDFP in humans is 43.9-65.2 mL/min/kg.

1.5 Rationale for Conducting the Trial

A safe, reliable therapy deployed early in the care of acute stroke patients, either ischemic or hemorrhagic, that restored critical oxygen supply to brain could potentially attenuate ischemic tissue damage and could improve long-term patient outcomes. Immediate restoration of critical brain oxygenation to bridge the time to vascular reperfusion by other methods would be expected to decrease ischemic damage, improve immediate outcomes, decrease sequelae, and reduce long-term health care costs.

DDFPe (2% w/vol dodecafluoropentane emulsion (NVX-208)) is a liquid fluorocarbon, which transports over 200 times as much oxygen per milligram of fluorocarbon as liquid fluorocarbons that were previously tested extensively as oxygen therapeutics¹³⁻¹⁵. It can easily be injected intravenously. Intravenous drug delivery in the first hour after the onset of the symptoms and signs of stroke has been proven practical in the FAST MAG clinical trial of acute strokes²⁰.

We hypothesize that administration of DDFPe will provide critical tissue oxygenation in acute stroke patients to decrease stroke volumes and symptoms in these patients.

The rationale for administering the doses evaluated is:

1. The dose levels are within the levels already tested in animals and humans^{6-11,16,17}. Volunteers received two IV bolus doses of 0.35 mL/kg of activated DDFPe 24 hours apart and brain cancer patients received daily doses of 0.17 mL/kg of unactivated DDFPe¹⁹.

Title: A phase 1b dose-finding study of DDFPe in acute ischemic stroke

PIs: [name] & [name]

Institution: UAMS

Sponsor: UAMS

2. Therapeutic reversal of tumor hypoxia has already been observed in patients administered doses of 0.1 mL/kg and 0.17 mL/kg^{19,21}.
3. Therapeutic reduction in stroke damage has been observed at dose levels of 0.1 mL/kg in rabbits⁶⁻¹¹. Since drug effects tend to correlate with body surface area/weight, one would predict that a dose of approximately 0.03 mL/kg should be effective in humans compared to rabbits. Therefore, we do not believe that it is necessary to explore doses higher than 0.17 mL/kg.

2.0 Objectives

2.1 Primary Objective

The primary objective of this study is to establish the Maximum Tolerated Dose (MTD) of DDFPe given intravenously at intervals of 90 ± 10 minutes x 3 doses within 12 hours after subjects have had a documented Acute Ischemic Stroke (AIS).

2.2 Secondary Objective

The secondary objective of this study is to assess the frequency and severity of adverse events following administration of DDFPe to patients who have had an AIS.

2.3 Exploratory Objective

We will evaluate the feasibility of using the National Institutes of Health Stroke Scale (NIHSS) to assess the immediate response to intravenous DDFPe in patients with AIS.

3.0 Study Design

[figure not shown]
3.1 Study Design

This study is a randomized, placebo controlled, blinded escalating dose study designed to determine the MTD and adverse events possibly related to intravenous administration of DDFPe. At each of three dose levels (0.05, 0.10, 0.17 mL/kg) six subjects will receive DDFPe and two will receive placebo.

3.2 Study Schema

The study flow is shown below in Figure 1:

Figure 1: Study Schema

4.0 **Trial Registration**

The trial will be registered in the ClinicalTrials.gov database prior to enrollment of the first subject. Updated information will be included in the record every six (6) months or as necessary. Results will be included in the ClinicalTrials.gov database within one (1) year after the completion of the study.

5.0 **Investigational Product**

5.1 Description of the Investigational Product

DDFPe (2% w/vol dodecafluoropentane emulsion (NVX-208)) is a liquid fluorocarbon, which transports over 200 times as much oxygen per milligram of fluorocarbon as liquid fluorocarbons that were previously tested extensively as oxygen therapeutics. The active ingredient dodecafluoropentane (DDFP) is a liquid with a boiling point of 28-30°C at atmospheric pressure. It is formulated as a nanodroplet dispersion of 2% (w/v) DDFP, stabilized by a 0.3% (w/v) fluorosurfactant, PEG Telomer B, in a continuous phase of 30% (w/v) sucrose.

Title: A phase 1b dose-finding study of DDFPe in acute ischemic stroke
PIs: [name] & [name]
Institution: UAMS
Sponsor: UAMS

Clinical supplies for this study have been manufactured under aseptic conditions at NuvOx Pharma in Tucson, Arizona, USA. DDFPe is produced as a stable emulsion, which is terminally filtered through 0.2 µm sterile filters, and aseptically sealed in vials containing 10 mL of DDFPe.

The placebo will be a sterile 1:101 dilution of Intralipid® 20% IV fat emulsion in aqueous sodium chloride (0.9% w/v) for injection prepared by pharmacy staff according to instructions in the Pharmacy Manual. Immediately prior to injection, the placebo will be aseptically compounded and placed directly into the same dispensing syringes as those for dispensing used for the injection of DDFPe^{22, 23}. The placebo will not be stored for any length of time.

5.2 Storage and Preparation of the Investigational Product

DDFPe will be shipped to the University of Arkansas for Medical Sciences (UAMS) Research Pharmacy prior to the start of the study along with instructions for handling, storage, dispensing and administration of DDFPe. All instructions are detailed in the Pharmacy Manual.

Receipt of drug in proper condition will be recorded by the research pharmacist. Upon receipt, any drug that does not meet the conditions established in the Pharmacy Manual or arrives with vials that are broken or otherwise damaged will be reported to NuvOx and instruction will be sought as to whether the vials can be used or should be set aside for later return or destruction. The site will be responsible for its own drug accountability.

DDFPe will be provided in 10 mL vials and stored upright at 2-8°C at ambient humidity in a monitored refrigerator prior to use. Once a subject has been identified, the drug may be removed from the refrigerator and stored at room temperature up to 6 hours until administered. The study drug may not be frozen. All vials of DDFPe will be labelled for investigational use. The number of vials stored in each locked kit will be calculated to allow for administration of the maximum dose at each dosing level. Each kit will also have a table used to calculate the dose, drug dosing and accountability forms and will be labeled for investigational use only. Immediately prior to injection, DDFPe or placebo will be prepared as per instructions in the Pharmacy Manual by pharmacy staff. The syringes containing either DDFPe or placebo will be appropriately labeled for investigational use only and provided to the clinical team in a blinded manner.

Once a kit has been opened, it should be returned to the pharmacy after use.

5.3 Dose Escalation Plan

5.3.1 Dose Escalation

The plan for dose escalation is shown in Table 5.1.

Cohort	DDFPe Dose (mL/kg)	Maximum Dose (mL)
1	0.05 (x 3 doses)	5 mL/dose x 3 doses
2	0.10 (x 3 doses)	10 mL/dose x 3 doses
3	0.17 (x 3 doses)	17 mL/dose x 3 doses

* Subjects weighing more than 100kg will be included in the study. Doses will be limited to a maximum based on a weight of 100 kg for subjects weighing in excess of 100 kg.

5.3.2 Dose Limiting Toxicity

Dose limiting toxicity (DLT) will be defined by the following criteria:

- Clinically significant changes in vital signs:
 - Heart rate \pm 50% from baseline
 - Respiratory rate >30 /min
 - Systolic blood pressure < 90 mmHg or >220 mmHg
 - Diastolic blood pressure >110 mmHg
- New (i.e. not seen at baseline) ECG changes consistent with:
 - Acute right ventricular dilation or strain
 - Incomplete or complete bundle branch block
 - Q waves in leads III and aVF
 - T-wave inversion and/or ST segment changes in the precordial leads
 - Any other clinically significant cardiac arrhythmia
- Common Terminology Criteria for Adverse Events (CTCAE) 4 Grade 3 or higher cough, dyspnea, chest pain-cardiac or non-cardiac, chest wall pain or hypoxia (See [Appendix 1](#) for specific criteria)
- NIHSS: sudden worsening of 4 or more from the baseline (pre-DDFPe initiation)
- The Medical Monitor will review all data collected at Post-Dose #3 (approximately 4-6 hours after the end of the Dose #3 infusion of DDFPe or placebo for each subject). Enrollment will be on hold until the Medical Monitor has reviewed the data and approves enrollment of an additional subject. The Medical Monitor may choose to temporarily halt the study if serious concerns arise regarding subject safety.

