Study Product, Dose, Route, Regimen	Dodecafluoropentane emulsion (DDFPe) Dose Range: 0.05, 0.10, and 0.17 mL/kg (Maximum dose: 17 mL/dose) Route: Intravenous over 5-10 minutes every 90 ± 10 minutes x 3 doses Placebo - Intralipid® 20% IV fat emulsion Dose: Sterile 1:101 dilution of Intralipid® in aqueous sodium chloride (0.9% w/v) Route: Intravenous over 5-10 minutes every 90 ± 10 minutes x 3 doses
Duration of Administration	Approximately 3-4 hours
Reference Therapy	None
Primary Outcome Measures	DLT (dose limiting adverse events) including clinically significant changes in vital signs, peripheral oxygen saturation (pulse oximetry), clinical symptoms, NIH Stroke Scale, laboratory values, and ECG measurements, Grade 3 or higher scores on selected CTCAE 4 measures

Title: A phase 1b dose-finding study of DDFPe in acute ischemic stroke

PIs: [name] & [name]

Institution: UAMS

Sponsor: UAMS

ABBREVIATIONS

AE	Adverse Event
AIS	Acute ischemic stroke
ALT	Alanine Aminotransferase
ANOVA	Analysis of Variance
aPTT	Activated Partial Thromboplastin Time
AST	Aspartate Aminotransferase
AUC	Area under the Concentration vs. Time Curve
BP	Blood Pressure
BUN	Blood Urea Nitrogen
CL	Clearance
Cmax	Maximum Concentration
COPD	Chronic Obstructive Pulmonary Disease
CRF	Case Report Form
CT	Computed (Computerized) Tomography
CTCAE	Common Terminology Criteria for Adverse Events
DDFP	Dodecafluoropentane
DDFPe	Dodecafluoropentane emulsion
DBP	Diastolic Blood Pressure
DLT	Dose Limiting Toxicity
DSM	Data Safety Monitor
ECG	Electrocardiogram
FDA	Food and Drug Administration
HIPAA	Health Insurance Portability and Accountability Act
HR	Heart rate
IEC	Independent Ethics Committee
INR	International Normalized Ratio
IRB	Institutional Review Board
IV	Intravenous
LAR	Legally Authorized Representative
LFT	Liver Function Tests
mmHg	Millimeters of Mercury
mRS	modified Rankin Scale
mSec	Millisecond
MTD	Maximum Tolerated Dose
N/A	Not Applicable
ND	Not Done
NIH	National Institutes of Health
NIHSS	National Institutes of Health Stroke Scale
NSAID	Non-Steroidal Anti-Inflammatory Drug
NYHA	New York Heart Association
OTs	Oxygen Transporters
PHI	Personal Health Information
PTB	PE-Telomer-B
RR	Respiratory Rate

Title: A phase 1b dose-finding study of DDFPe in acute ischemic stroke

PIs: [name] & [name]

Institution: UAMS

Sponsor: UAMS

SAE	Serious Adverse Event
SBP	Systolic Blood Pressure
SD	Standard Deviation
Tmax	Time at Which the Maximum Concentration (Cmax) Occurs
tPA	Tissue Plasminogen Activator

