5.3.3 Maximum Tolerated Dose

The algorithm for determining the MTD is as follows:

- Up to six subjects and two controls will be enrolled at each dose level constituting each cohort. Subjects will be evaluated for four hours after receiving the last of the three doses and again at discharge from the hospital or one week later, whichever is sooner.
- DLT is previously defined in [Section 5.3.2](#).
- If no DLTs are observed in a patient at Post-Dose #3 of DDFPe or placebo the Medical Monitor may allow progression to the next patient.

- After all 8 subjects have been enrolled in a cohort, the Medical Monitor will review the data. A decision as to whether the study may proceed to the next cohort will be made.
- If a total of two or fewer subjects in an 8 subject cohort experience a DLT, escalation to the next cohort may proceed if approved by the Medical Monitor. If three or more DLTs were observed, the Medical Monitor may consult with the Research Pharmacist to determine if the observed DLTs occurred in subjects who received DDFPe or placebo. If any of the DLTs were observed in the subjects receiving placebo, the Medical Monitor may allow the study to proceed as long as two or fewer subjects with DLTs received DDFPe.
- If three or more subjects who received DDFPe in an 8 subject cohort experience a DLT, the MTD will be determined to have been exceeded and further enrollment in the cohort as well as dose escalation will stop. The dose administered to the previous cohort will be considered to be the MTD.
- Subjects who withdraw from the study for reasons other than a DLT may be replaced.
- The Medical Monitor will review all safety data for each patient and cohort and must grant approval before proceeding to the next patient and/or cohort.
- Exploration of lower dose levels intermediate to a level previously shown to be well tolerated may be considered. In addition to reducing the dose, this might include reducing the number of doses, increasing the time between doses, and/or altering the infusion time.
- The dose exploration will be complete when either: (1) the MTD has been defined or (2) when no MTD has been reached but six subjects and two controls have been treated at the last cohort level approved by the Medical Monitor.

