6.3.11 Pneumonia, bronchitis, or other acute respiratory disease

6.3.12 Current anticoagulant therapy except for antiplatelet therapy (aspirin, NSAIDs) and prophylactic doses of low molecular weight heparin to prevent deep vein thrombosis. Note: tPA administered as part of subjects' therapy for AIS is allowed. However, thrombolytic therapy is not a study requirement.

6.3.13 History of allergic reaction attributed to compounds of similar chemical composition to DDFPe or soy or egg allergies (see Investigator's Brochure).

6.3.14 Subject has received any investigational drug within thirty (30) days prior to enrollment into the study

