7.5.7 NIH Stroke Scale

The NIHSS will be administered during Screening to assure that subjects score between 2 and 20, inclusive, to meet the study Inclusion criteria. Initial NIHSS scores from outside originating hospitals or facilities are acceptable only if performed by a certified neurologist. The NIHSS will be repeated throughout the study as indicated in the Schedule of Time and Events (Appendix 4). The NIHSS may be found at:

https://www.ninds.nih.gov/doctors/NIH_Stroke_Scale.pdf

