7.6 Day 1: Study Procedures

After documentation that the subject passed the screening procedures and meets all Inclusion and Exclusion criteria, study personnel will check to assure that a patent intravenous catheter is in place for infusion of the DDFPe. The catheter should be used solely for infusion of DDFPe and compatible intravenous fluids during the study intervention period (from the initiation of Dose #1 to after the Dose #3 infusion is complete).

Dose #1: DDFPe will be ordered from the pharmacy and prepared as previously described. The time that the infusion begins will be recorded. The drug or placebo will be infused over 5-10 minutes. At the end of the infusion, the time will again be recorded. Vital signs and pulse oximetry will be monitored. Measurements will be recorded every 15 minutes. The subject will be observed for any signs of adverse events for 90 minutes after the completion of the infusion.

Dose # 2: Any new concomitant medications will be recorded. The second dose of DDFPe or placebo will be administered as previously described over 5-10 minutes. Times will be recorded at the beginning and end of the infusion as before. Vital signs and pulse oximetry will be monitored. Measurements will be recorded every 15 minutes. The NIHSS will be repeated within 60 minutes after the end of the DDFPe infusion. The subject will be observed for any signs of adverse events for 90 minutes after the completion of the infusion.

Dose #3: Any new concomitant medications will be recorded. The third dose of DDFPe or placebo will be administered as previously described over 5-10 minutes. Times will be recorded at the beginning and end of the infusion as before. Vital signs and pulse oximetry will be monitored. Measurements will be recorded every 15 minutes. The NIHSS will be repeated within 60 minutes after the end of the DDFPe

infusion. The subject will be observed for any signs of adverse events for 90 minutes after the completion of the infusion.

Vitals should be taken at all scheduled time points (i.e. every 15 minutes); however, deviations from scheduled times will not be considered protocol deviations. The exact date and time of each measurement will be recorded on the CRF.

Post-Dose #3: Approximately 4 ± 1 hours after the end of Dose #3, the following observations will be made:

- Concomitant medications administered after Dose #3
- A brief physical examination
- Vital signs (BP, HR, RR)
- Pulse oximeter measurement
- NIHSS
- ECG

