Appendix 4: Schedule of Time and Events

	Day 1					Day 4	Day 7±1 or Day of Discharge	Day 30 ±7	Day 90 ±14
Study Procedures	Screening (Baseline)	Dose #1 ^a	Dose #2 ^a	Dose #3 ^a	Post- Dose #3 ^b				
Informed Consent	X								
I/E Criteria	X								
Concomitant Meds	X	X	X	X	X				
Medical History ^c	X						X	X	X
Physical Exam ^c	X				X		X	X	
Weight	X								
Vital Signs ^d	X	X	X	X	X		X	X	
Pulse Oximetry ^e	X	X	X	X	X		X		
Modified Rankin Scale	X						X	X	X
NIHSS	X		X ^f	X ^f	X		X	X	
ECG ^g	X				X		X		
Pregnancy Test ^h	X								
Lab Studies ⁱ	X				X		X		
Administer DDFPe ^j		X	X	X					
Adverse Events		X	X	X	X	X	X	X	X

a Each dose of DDFPe or placebo is to be administered intravenously over 5-10 minutes. Start and stop times will be recorded as will the volume infused.

b Post-dose #3 concludes approximately 4-6 hours after the end of the Dose #3 infusion.

c Brief, targeted medical history and physical exam.

d Vital signs (blood pressure, heart rate, respiratory rate) will be done every 15 minutes through the end of Post-Dose #3 (approximately 4-6 hours) and then consistent with standard procedures for the hospital unit. Temperature will be done every 1-4 hours consistent with the hospital unit standard procedures.

e Continuous or spot readings may be taken; if continuous readings are used, record the measurement every 15 minutes.

f To be performed within 60 minutes following the dose.

g 12-lead ECG to be examined at the bedside by the study personnel and later reviewed by a board certified cardiologist.

h Serum pregnancy test will be done in pre-menopausal women.

i To include: CBC, electrolytes (Na, K, Cl), BUN, creatinine, LFTs, calcium, albumin, glucose

j DDFPe or placebo to be administered over 5-10 minutes intravenously through a peripheral or central IV. The interval between the end of one dose and the beginning of the next should be 90 ± 10 minutes.

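### The DLT in the primary outcome and the DLT that sets the MTD differ on laboratory values, and the NIHSS DLT may be measured from an outside hospital's score

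*Combined protocol and SAP*

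**What the plan says.** **Laboratory values.** The Primary Outcome Measures row of the Study Summary reads "DLT (dose limiting adverse events) including clinically significant changes in vital signs, peripheral oxygen saturation (pulse oximetry), clinical symptoms, NIH Stroke Scale, laboratory values", and goes on to ECG and selected CTCAE items. Section 5.3.2 gives the DLT criteria as a list: vital signs, new ECG changes, Grade 3 or higher cough, dyspnea, chest pain, chest wall pain or hypoxia, and NIHSS. No item on it is a laboratory result, and Appendix 1 contains no laboratory term. Section 5.3.3 takes its DLT from 5.3.2 and applies the rule "If three or more subjects who received DDFPe in an 8 subject cohort experience a DLT", at which point the dose is declared above the MTD. Laboratory tests are drawn at Post-Dose #3 (7.6) and at Day 7 or discharge (7.8).

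**NIHSS baseline.** The criterion in 5.3.2 is "NIHSS: sudden worsening of 4 or more from the baseline (pre-DDFPe initiation"). The only NIHSS that Appendix 4 places before dosing is in the Screening (Baseline) column. Section 7.5.7 says the scale is administered during screening, then adds: "Initial NIHSS scores from outside originating hospitals or facilities are acceptable only if performed by a certified neurologist". Section 7.6 has no NIHSS at Dose #1. At Dose #2 it says "The NIHSS will be repeated within 60 minutes after the end of the DDFPe infusion", and the Appendix 4 footnote agrees: "To be performed within 60 minutes following the dose". On thrombolysis, 6.3.12 notes that "tPA administered as part of subjects' therapy for AIS is allowed".

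**The concern.** DLT is the primary outcome and also the only event counted in the MTD rule, so its definition should be single and its reference point fixed.

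On laboratory values, the two places give different answers. A serious laboratory abnormality at Post-Dose #3 belongs to the primary outcome under the Study Summary, yet adds nothing to the count of three under 5.3.2. Because it is not a DLT there, 5.3.3 would also let a subject withdrawn for it be replaced.

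On the NIHSS, a baseline scored at another hospital may predate transfer, thrombolysis and several hours of an evolving stroke. Section 10.4(e) itself expects placebo scores to move when reperfusion succeeds or occurs spontaneously. Change that took place before any study drug could then be attributed to DDFPe, or could cancel a real worsening after it. In a cohort of six DDFPe subjects, one such error can decide whether escalation continues.

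**Working it through.** The plan states no DLT rate, power or error rate (10.1 says no sample size estimates were done), so there is no planned figure to reproduce.

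**Step 1: match the Study Summary's DLT components to 5.3.2.**
- Vital signs: present.
- Oxygen saturation: covered by CTCAE hypoxia.
- Clinical symptoms: covered by cough, dyspnea and the chest pain terms.
- NIHSS: present.
- ECG: present.
- Laboratory values: no counterpart in 5.3.2 or Appendix 1.

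Laboratory values are the only component left unmatched.

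**Step 2: how long the NIHSS is unobserved.** Infusions last 5 to 10 minutes, and the gap from the end of one to the next is 90 ± 10 minutes (5.5).
- Start of Dose 1 to the NIHSS after Dose #2: at the earliest 5 + 80 + 5 = 90 min; at the latest 10 + 100 + 10 + 60 = 180 min.
- Whole course: 3×5 + 2×80 = 175 min to 3×10 + 2×100 = 230 min.
- Upper bound on the age of an outside score at Dose 1, if scored at onset: 720 − 230 = 490 min (8.2 h) to 720 − 175 = 545 min (9.1 h) if all three doses must fall within 12 hours (2.1), or up to 12 h if only entry must (Study Summary). Real ages would be shorter.

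**Step 3: what a stale baseline does.** Let B0 be the outside score, B1 the unrecorded score just before Dose 1, and S the score after Dose #2. The recorded change is S − B0 = (S − B1) + (B1 − B0). Only S − B1 relates to study drug.
- False DLT: with S = B1, a pre-dose rise of 4 already meets the threshold.
- Masked DLT: a true worsening of exactly 4 is hidden by a pre-dose fall of 1.

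A difference between raters enters B1 − B0 in the same way.

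**Step 4: leverage of one error under the three-of-six rule.** DLT rates p are assumed; X is the number of DLTs. Correctly classified, P(X ≥ 3 of 6) is 1.6% at p = 0.10 and 25.6% at p = 0.30.

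Now condition on one subject's true status:

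| p | Subject has no DLT: P(X ≥ 3 of 5) | Subject has a DLT: P(X ≥ 2 of 5) |
|---|---|---|
| 0.10 | 0.0086 | 0.0815 |
| 0.30 | 0.1631 | 0.4718 |

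These average back to the unconditional values: 0.9×0.0086 + 0.1×0.0815 = 0.0159, and 0.7×0.1631 + 0.3×0.4718 = 0.2557. A false DLT moves the cohort from the left column to the right (0.9% to 8.1%; 16% to 47%). A masked DLT moves it from right to left by the same amount.

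**Step 5: illustration over assumed error rates.**
- A fraction q of subjects without a DLT wrongly counted, so p′ = p + (1 − p)q. For q = 1%, 5%, 10%, the stopping probability goes from 1.6% to 2.0%, 4.3%, 8.7% at p = 0.10, and from 25.6% to 26.9%, 32.3%, 39.4% at p = 0.30.
- A fraction m of true DLTs missed, so p′ = p(1 − m). At p = 0.30, m = 10%, 25%, 50% takes 25.6% down to 20.2%, 13.2%, 4.7%.

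None of p, q or m comes from the documents.

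**The case against.** **The MTD rule is not ambiguous.** A reader might infer from the laboratory mismatch that the algorithm has two competing definitions, or that laboratory toxicity could go unseen. Neither follows. Section 5.3.3 points to 5.3.2 alone. The Medical Monitor reviews all Post-Dose #3 data, may halt the study, and "must grant approval before proceeding to the next patient and/or cohort". That objection stands, and it limits this part to a disagreement between the stated primary outcome and the operative definition. It does not settle which events the primary outcome contains.

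**The outside-score sentence concerns eligibility.** It sits in text about the 2 to 20 entry range, is limited to certified neurologists, and follows a statement that the scale is given during screening. The pre-DDFPe wording could also be taken to mean a fresh score. But no fresh score is scheduled and no repeat is required, so an outside score can be the only one on record. Certification speaks to the rater's competence, not to the age of the score or a change of rater. It would go too far to say that outside scores will be the DLT baseline; the text supports only that they may be.

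**Judgement can filter errors.** The word sudden lets a reviewer discount slow drift, and subjects are observed for 90 minutes after each infusion. This helps with obvious events. Sudden is undefined, however, and the scheduled scores cannot place a change before or after Dose 1.

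**Few subjects may be affected.** This may well be so. Section 10.4 expects fewer than 20% of 24 to receive reperfusion therapy (0.20 × 24 = 4.8, so at most 4 if that expectation holds). That count includes placebo subjects and those scored on site or treated after Dose 1. Successful reperfusion should lower scores, so this route mainly masks DLTs rather than creating them. Transfers are not counted anywhere.

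**The exploratory analysis is little touched.** Its main comparison is restricted to DDFPe started under 3 hours from last known well, so an outside score there is under 3 hours old, and 10.4 names no reference score. I put no weight on this consequence.

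**Conclusion.** Both parts hold as textual defects and should be fixed.

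The Study Summary's primary outcome includes laboratory values and the operative DLT definition does not. This has no numerical size and does not make the MTD rule indeterminate, but the passages must be reconciled.

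The NIHSS DLT can rest on an outside score of unspecified age, with no scheduled score between screening and the one 90 to 180 minutes after Dose 1 starts. The error can run in either direction, and its frequency cannot be derived from the documents. What can be shown is leverage: one misclassified DDFPe subject shifts the chance of stopping between 0.9% and 8.1% at an assumed 10% DLT rate, or between 16% and 47% at 30%. Those pairs are conditional on that subject's true status; the unconditional values with no error are 1.6% and 25.6%. A reader might take these figures, or those under assumed error rates, as estimates of how often the MTD would be wrong. They are illustrations only, and any three-of-six rule would show similar sensitivity.

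**What to change.** 1. Make the Study Summary and 5.3.2 list the same DLT components. Whether laboratory criteria are included, and at what thresholds, is for the sponsor to decide.
2. State in 7.5.7 that an outside NIHSS serves eligibility only.
3. Require an on-site NIHSS before Dose 1 when the screening score came from outside, or when reperfusion therapy was given after the screening score. The second condition matters because an on-site score taken before thrombolysis has the same weakness.
4. Name the last on-site NIHSS before Dose 1 in 5.3.2 as the DLT baseline, and add a footnote to the NIHSS row of Appendix 4.

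The cost is a few sentences and one short bedside NIHSS in the subjects concerned, arranged so that it does not delay dosing. Sample size and study duration do not change.
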